### Table 14.2.4.1.2 Post-hoc Analysis: Time to Sustained Withdrawal of Oxygen Supplementation - Multivariate Analysis using a Random Forest Approach (Intent-To-Treat Population)

Variable	Parameter Estimate	Standard Error	p-value	Hazard Ratio
XXXXXXXXXXXXXXXX XXXXXXXXXXXXXXXXXXXXX	X.XXXX X.XXXX X.XXXX	X.XXXX X.XXXX X.XXXX	X.XXXX X.XXXX X.XXXX	X.XXX X.XXX X.XXX

Notes: Sustained withdrawal of oxygen supplementation (in days) with no subsequent reutilisation during remaining study period is defined as the first day, from randomisation through completion of the study, on which a patient

i. satisfies categories 0 to 4 on the 11-point WHO Clinical Progression Scale, and

ii. has no subsequent reutilisation of oxygen supplementation (5 to 10 on the 11-point WHO Clinical Progression Scale)

If the patient is discontinued between day 15 and day 31 visits, and there is an attempt of contact and study discontinuation on or after the day 31 visit due date, the patient is censored at day 31. [a] Parameter Estimate, Standard Error, p-value, and Hazard Ratio based on a Cox proportional-hazards regression model with treatment group, and Baseline IL-10 (continuous) as covariates.

Programming notes (not part of the table):

- The displayed xxx do not reflect actual decimal precision. Please follow Section 2.11 for rounding rules.
- Force to include the treatment arm in addition to the covariates.

• Include the prognosis factors identified by Pharma Mar using a random forest approach as covariates in the modelling and the footnote.

Variable	Parameter Estimate	Standard Error	p-value	Hazard Ratio
XXXXXXXXXXXXXXXX XXXXXXXXXXXXXXXXXXXXX	X.XXXX X.XXXX X.XXXX	X.XXXX X.XXXX X.XXXX	X.XXXX X.XXXX X.XXXX	X.XXX X.XXX X.XXX

Table 14.2.4.2.1 Post-hoc Analysis: Time to Sustained Hospital Discharge - Multivariate Analysis (Intent-To-Treat Population)

Notes: Sustained (ie, with no subsequent readmission to Day 31) hospital discharge (in days), defined as the first day, from randomisation through completion of the study, on which a patient

i. discharges from the hospital, and

ii. has no subsequent re-admission

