#### 2.1.3.3 Other Secondary Objectives

The other efficacy secondary objectives of this study are

- To compare efficacy of plitidepsin 1.5 mg or 2.5 mg versus the control in terms of hospital readmission related to COVID-19.
- To compare efficacy of plitidepsin 1.5 mg or 2.5 mg versus the control in terms of clinical evolution.
- To compare efficacy of plitidepsin 1.5 mg or 2.5 mg versus the control in terms of the need of supplementary oxygen.
- To compare efficacy of plitidepsin 1.5 mg or 2.5 mg versus the control in terms of the need of intensification of respiratory or intensive care support.
- To compare efficacy of plitidepsin 1.5 mg or 2.5 mg versus the control in terms of the need of intensification of pharmacological therapies.
- To compare efficacy of plitidepsin 1.5 mg or 2.5 mg versus the control in terms of superinfections.
- To compare efficacy of plitidepsin 1.5 mg or 2.5 mg versus the control in terms of mortality.
- To compare efficacy of plitidepsin 1.5 mg or 2.5 mg versus the control in terms of the evolution of viral load.
- To compare efficacy of plitidepsin 1.5 mg or 2.5 mg versus the control in terms of the evolution of inflammatory markers.
- To compare efficacy of plitidepsin 1.5 mg or 2.5 mg versus the control in terms of the immune response against severe acute respiratory syndrome coronavirus 2 (SARS-CoV-2).
- To compare efficacy in the primary endpoint and describe safety/tolerability of pooled plitidepsin arms versus control.
- To compare efficacy in the primary endpoint and describe safety/tolerability between plitidepsin arms (1.5 versus 2.5 mg) in case both are significantly superior to the control.
- To explore the influence of risk factors or scores for clinical deterioration that were not individually included.
- To compare the results obtained before and after the change of the primary and key secondary endpoint (protocol v.6 versus v.7).

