- Hypertension at Screening, defined as Hypertension (Standardised MedDRA Query [SMQ]) in the Medical History form: Yes or No
- Individual co-morbidities included in the Charlson Index: myocardial infarction (Yes or No), congestive heart failure (Yes or No), peripheral vascular disease (Yes or No), cerebrovascular disease (Yes or No), dementia (Yes or No), chronic obstructive pulmonary disease (Yes or No), connective tissue disease (Yes or No), peptic ulcer disease (Yes or No), liver disease ('None', 'Mild' or 'Moderate or Severe'), diabetes mellitus ('None or diet controlled', 'Uncomplicated' or 'End-organ damage'), hemiplegia (Yes or No), moderate or severe chronic kidney disease (Yes or No), solid tumor ('None', 'Localized' or 'Metastatic'), leukemia (Yes or No), lymphoma (Yes or No) or AIDS (Yes or No).
- ISARIC-4C mortality score: Low (0 3), Intermediate (4 8), High (9 14) or Very high (≥ 15)
- ISARIC-4C deterioration probability (%): `≤ 25', `(25 50]', or `> 50'
- Lactate dehydrogenase (LDH) at Baseline: ≤ ULN or > ULN

- CRP (mg/L) at Baseline: ≤ 100 or > 100
- D-dimer at Baseline: ≤ ULN or > ULN
- Ferritin at Baseline: ≤ ULN or > ULN
- Creatinine at Baseline: ≤ ULN or > ULN
- IL-6 at Baseline: ≤ Median or > Median value (at the analysis time cutoff may be updated based on distribution values if needed)
- IL-10 at Baseline: ≤ Median or > Median value (at the analysis time cutoff may be updated based on distribution values if needed)
- Lymphocytes count decreased at Baseline: 'Grade 0' or 'Grade  $\geq 1'$
- Neutrophils/lymphocytes ratio at Baseline:  $< 6 \text{ or } \ge 6$
- SARS-CoV-2 variant: Alpha, Beta, Gamma, Delta, Eta, Iota, Kappa, Lambda, Mu, or any potential new variant

The same covariates used for the primary efficacy endpoint analysis will be used for the subgroup analyses.

For ISARIC-4C mortality score and deterioration probability calculation:

- A Glasgow coma scale score of 15 is assumed for all the patients.
- Urea (mmol/L) will be calculated as blood urea nitrogen (mmol/L) \* 60 / 28.

Forest plots of the hazard ratios, and the 95% CI for the comparison of each dose of plitidepsin versus control arm will be presented by endpoint for all subgroups using the ITT population.

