#### 7.6.5 Exploratory Analysis

A multivariate analysis will be performed for the primary and key secondary efficacy endpoint, including the treatment group, randomisation stratification factors and all the above subgroup variables as covariates. Those covariates with more than 10% of missing values will be omitted from the multivariate analysis. A stepwise selection model will be used, with significant level equal to 0.2 and 0.05, to enter into the model and to remain in the model, respectively.Treatment group will be forced to be included in addition to the significant covariates.

Time-to sustained withdrawal of oxygen supplementation will be compared between each dose of plitidepsin versus control arm receiving the antiviral control arm, ie, the regulatory-approved antiviral for those patients randomised to the control arm (remdesivir or favipiravir).

Time-to sustained withdrawal of oxygen supplementation will be analysed using the Kaplan-Meier method and 25th percentile, median and 75th percentile time will be presented for the plitidepsin arms and control arm receiving the antiviral control

Sponsor Name: Pharma Mar S.A. Sponsor Protocol ID: APL-D-003-20

arm, together with 95% CIs. The 95% CIs will be computed based on Brookmeyer-Crowley method and using a log log transformation. The mean time to sustained withdrawal of oxygen supplementation and its standard error will be also presented for the pooled plitidepsin arms and control arm.

Time-to sustained withdrawal of oxygen supplementation between each dose of plitidepsin versus control arm receiving the antiviral control arm will be compared using a stratified log-rank test, including the randomisation stratification factors as covariates, ie, Geographical Region (Europe vs. Rest of the World), Charlson Comorbidity index (0-1 vs. >1) and pre-baseline Barthel index ( $\geq$ 90 versus <90) as derived using the eCRF data. The 2-sided p-values for the comparison of the pooled plitidepsin arms versus control arm will be presented.

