[a] Parameter Estimate, Standard Error, p-value, and Hazard Ratio based on a Cox proportional-hazards regression model with treatment group, randomisation stratification factors, ie, geographical region (Europe, Rest of the World), Charlson Comorbidity Index (0 - 1, > 1) and pre-baseline Barthel index ( $\geq 90$  versus < 90) as derived using the eCRF data, and patients included before and after amendment (Protocol v.6 or before, Protocol v.7), sex (female, male), age at study entry (18 to 39, 40 to 64,  $\geq$  65 years), race (asian, black, white, other), ethnic group (Hispanic or Latino, Not Hispanic or Latino), site location (Site XXX, Site XXX, Other Sites), use of antiviral therapies or immunomodulatory drugs through the study (Yes, No), previous COVID-19 vaccination status (Fully vaccinated, Non-fully vaccinated), anti-SARS-CoV-2 IgG at Day 1 (Non-positive, Positive), pre-randomisation dexamethasone (Yes, No), total duration of corticoid therapy ( $\leq$  9 days, [9 - 11] days, > 11 days), total cumulative dose of corticoid therapy (dexamethasone or equivalent) ( $\leq$  60 mg, > 60 mg), SARS-CoV-2 viral load (log10 copies/mL) at Day 1 before study drug administration ( $\leq 4$ , [4 - 7], > 7), time between onset date of COVID-19 symptoms and initiation of study treatment ( $\leq 5$  days, 6 - 10 days, > 10 days), body mass index (kg/m2) at Screening (< 30,  $\geq$  30), hypertension at Screening (Yes, No), myocardial infarction (Yes, No), consective tissue disease (Yes, No), periptic ulcer disease (Yes, No), liver disease (Yes, No), cerebrovascular disease (Yes, No), dementia (Yes, No), thronic obstructive pulmonary disease (Yes, No), moderate or severe chronic kidney disease (Yes, No), solit tumor (None, Localized, Metastatic), leukemia (Yes, No), lymphoma (Yes, No), AIDS (Yes, No), ISARIC-4C mortality score (Low (0 - 3), Intermediate (4 - 8), High (9 - 14), Very high ( $\geq 15$ )), ISARIC-4C deterioration probability ( $\leq 25$ , (25 - 50], > 50), LDH at Baseline ( $\leq$  ULN, > ULN), creatinine at Baseline ( $\leq$  ULN, > ULN)

- The displayed xxx do not reflect actual decimal precision. Please follow Section 2.11 for rounding rules.
- Omit those covariates with more than 10% of missing values from the multivariate analysis.
- Force to include the treatment arm in addition to the significant covariates.

Variable	Parameter Estimate	Standard Error	p-value	Hazard Ratio

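### The exploratory stepwise Cox models enter numerically recorded covariates only as two- or three-level cuts, which wastes information, and the addendum codes IL-10 in two ways for the same endpoint

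*SAP*

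**What the plan says.** SAP 7.6.5 specifies a multivariate Cox model for the primary and the key secondary endpoint, with treatment group, the "randomisation stratification factors and all the above subgroup variables as covariates". Selection is automatic: "A stepwise selection model will be used, with significant level equal to 0.2 and 0.05, to enter into the model" and to stay, respectively, with treatment forced in. The shells are Tables 14.2.4.1 and 14.2.4.2, repeated in the addendum as Tables 14.2.4.1.1 and 14.2.4.2.1.

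The categories come from 7.6.4 and recur in the table footnotes:

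- **Three levels:** age, as in "sex (female, male), age at study entry (18 to 39, 40 to 64" and 65 or over; "SARS-CoV-2 viral load (log10 copies/mL) at Day 1 before study drug administration" (below 4, 4 to 7, above 7); "time between onset date of COVID-19 symptoms and initiation of study treatment" (up to 5, 6 to 10, above 10 days).
- **Two levels:** BMI at 30; CRP at 100 mg/L; LDH, D-dimer, ferritin and creatinine at the upper limit of normal; IL-6 and IL-10 at the median.

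The neutrophil/lymphocyte ratio (cut at 6) and the two ISARIC-4C scores are categorised too. For IL-6 and IL-10, 7.6.4 adds to the median "value (at the analysis time cutoff may be updated based on distribution values if needed".

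Addendum Table 14.2.4.1.2, for the same endpoint as Table 14.2.4.1.1, uses a "model with treatment group, and Baseline IL-10 (continuous) as covariates".

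**The concern.** Cut-points are needed to draw a forest plot, but not to fit a regression. In the Cox model, a patient just above a cut is treated like the most extreme patient in that group and unlike a patient just below it. The SAP gives no reason for this coding, and the numbers are available. Age and BMI are summarised as continuous (7.4), Day 1 viral load is a continuous covariate in the ANCOVA (7.6.2.3), and the analytes have units and decimal precision (TFL shells, Appendix 1).

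Three things are at stake:

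- the precision of each factor's estimate;
- the completeness of the adjustment behind the reported treatment HR;
- stepwise decisions that depend on where a cut falls. IL-10 could drop out of one addendum table and be significant in the next because of its coding.

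**Working it through.** The SAP states no figure for information loss, so there is none to reproduce. The check has four parts.

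**1. Formula.** For a normal covariate with a log-linear effect, the share of information kept is the between-category variance divided by the total variance.

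- Two levels, smaller group of share p: φ(z_p)² / [p(1−p)].
- Three levels: Σ [φ(a_i) − φ(a_{i+1})]² / p_i, where the a_i are the category limits on the standard normal scale.

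The category shares are assumptions, except that IL-6 and IL-10 are split 50/50 if the median is kept.

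**2. Results.**

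- Median split: 0.3989² / 0.25 = 0.637 kept, so 36.3% lost.
- 15/85 split: 0.2332² / 0.1275 = 0.426 kept, so 57.4% lost.
- Best three-level split, 27/46/27: 2 × 0.3306² / 0.27 + 0 = 0.810 kept, so 19.0% lost.

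| Coding | Assumed split | Information lost |
|---|---|---|
| Two levels | 50/50 | 36.3% |
| Two levels | 30/70 | 42.4% |
| Two levels | 20/80 | 51.0% |
| Two levels | 15/85 | 57.4% |
| Two levels | 10/90 | 65.8% |
| Three levels | 27/46/27 | 19.0% |
| Three levels | tertiles | 20.7% |
| Three levels | 10/50/40 | 23.0% |
| Three levels | 5/50/45 | 26.8% |
| Three levels | 10/80/10 | 38.4% |

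With the SAP's own age cuts, an assumed mean of 57 or 65 years and SD 14, the loss is 24% or 29%. With its symptom-duration cuts, an assumed mean of 7 days and SD 2.5, the loss is 25%.

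**3. Sensitivity to shape.** A median split loses 25% for a uniform covariate and 73% for a lognormal with log-SD 1 left on the raw scale. The floors of 36% and 19% therefore hold under normality, not in general.

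**4. Power, as illustration only.** Power for one factor tested alone at two-sided 0.05 is Φ(|ln HR| × √(D × share kept) − 1.96). SAP section 8 says recruitment stopped before 33% of events, and 0.33 × 530 ≈ 175. The final count D is not given, so a range is shown for an assumed HR of 0.80 per SD:

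| Events D | Continuous | Median split | 15/85 split |
|---|---|---|---|
| 100 | 61% | 43% | 31% |
| 150 | 78% | 59% | 43% |
| 175 | 84% | 65% | 49% |
| 200 | 88% | 71% | 54% |

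Worked case for D = 150, continuous: 0.2231 × 12.25 − 1.96 = 0.77, and Φ(0.77) = 78%. The ordering is the same at every D.

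**The case against.** The strongest reply is that this is an exploratory model with no confirmatory claim, and that the primary analysis is a stratified log-rank test using only the three stratification factors. That is correct and limits the weight. It does not justify the coding, because the tables still report a p-value and an HR for each retained factor and for treatment.

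A reader might infer that the coding defeats the secondary objective "To explore the influence of risk factors or scores for clinical deterioration that were not individually included". The SAP does not support that: 7.6.2.3 assigns this objective to the subgroup analysis of 7.6.4, where cuts are appropriate.

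A reader might also infer that the ULN cuts leave few patients on one side, or that 175 is a ceiling on the events. The SAP gives no covariate distributions. Patients already enrolled when recruitment stopped could still have events during follow-up to Day 31. Both points remain assumptions.

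The power figures describe a single covariate at 0.05, not stepwise selection among dozens of candidates, so they show direction rather than the performance of this model.

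On IL-10, Table 14.2.4.1.2 is a separate post-hoc model built on factors that the sponsor identified by random forest. The two codings are not a contradiction in the strict sense. They do show that continuous entry was feasible, and they leave two tables for one endpoint that cannot be compared on this factor.

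Finally, continuous terms bring their own choices: functional form, and the handling of values at quantification limits. This stands, and the fix must settle both in advance.

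**Conclusion.** The point holds as a cheap improvement of minor weight. Eleven numerically recorded covariates enter the stepwise Cox models only as cuts. Assuming normality and a log-linear effect, the eight two-level covariates each lose at least about 36% of their information. The three three-level covariates lose at least about 19%, and typically 19-30%.

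A single range such as 36-60% for all of them would be wrong. It fits two-level cuts with splits no more extreme than about 13/87. A three-level cut reaches it only when roughly 80% or more of patients fall in one level.

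The effect on the adjusted treatment HR cannot be sized from the SAP, and randomisation limits any systematic imbalance. Movable cutoffs concern IL-6 and IL-10 only. The primary stratified log-rank test is unaffected.

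**What to change.** In SAP 7.6.5 and the footnotes of Tables 14.2.4.1, 14.2.4.2, 14.2.4.1.1 and 14.2.4.2.1:

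- Enter the eleven covariates, the neutrophil/lymphocyte ratio and the ISARIC-4C scores as continuous terms. Keep viral load on its existing log10 scale, and log-transform CRP, LDH, ferritin, D-dimer, creatinine, IL-6 and IL-10.
- Fix the functional form in advance, either linear or a 3-knot spline, so that it is not chosen from the results.
- State one rule for values at quantification limits in these models. SAP 7.6.2.3 uses half the limit for viral load summaries and 7.7.3 uses the limit itself for laboratory values; neither is stated for this model.
- Code IL-10 the same way in Tables 14.2.4.1.1 and 14.2.4.1.2.
- Keep the cuts for the forest plots only.
- Label the run as supplementary, because the database was locked on 26 April 2023.

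The cost is SAP wording and minor programming. HRs are then read per unit or per doubling instead of above versus below a cut, and linearity needs a check.

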### Table 14.2.4.2 Time to Sustained Hospital Discharge - Multivariate Analysis (Intent-To-Treat Population)

Notes: Sustained (ie, with no subsequent readmission to Day 31) hospital discharge (in days), defined as the first day, from randomisation through completion of the study, on which a patient

i. discharges from the hospital, and

ii. has no subsequent re-admission

- The displayed xxx do not reflect actual decimal precision. Please follow Section 2.11 for rounding rules.
- Omit those covariates with more than 10% of missing values from the multivariate analysis.
- Force to include the treatment arm in addition to the significant covariates.

### Table 14.2.4.3.1 Time to Sustained Withdrawal of Oxygen Supplementation - Control Arm with Antiviral (Intent-To-Treat Population)

Variable	Plitidepsin 2.5mg (N=XXX)	Plitidepsin 1.5mg (N=XXX)	Control Arm with Antiviral [a] (N=XXX)
Patients who Reported Sustained Withdrawal of Oxygen			\
Supplementation, n (%)	xxx (xx.x)	xxx (xx.x)	xxx (xx.x)
Censored Patients, n (%)	xxx (xx.x)	xxx (xx.x)	xxx (xx.x)
Time-to Sustained Withdrawal of Oxygen Supplementation (days) 95% CI [b]			
25th percentile	xx.x (xx.x, xx.x)	xx.x (xx.x, xx.x)	xx.x (xx.x, xx.x)
Median	xx.x (xx.x, xx.x)	xx.x (xx.x, xx.x)	xx.x (xx.x, xx.x)
75th percentile	xx.x (xx.x, xx.x)	xx.x (xx.x, xx.x)	xx.x (xx.x, xx.x)
Mean (SE)	xx.x (xx.x)	xx.x (xx.x)	xx.x (xx.x)
Stratified Log-Rank Test			
2-sided p-value [c]	X.XXX	X.XXX	
Supportive Analysis - Stratified Cox Regression Model			
Hazard Ratio [d,e]	X.XXX	X.XXX	
95% CI for Hazard Ratio [d,e]	x.xxx - x.xxx	x.xxx - x.xxx	
2-sided p-value [d]	X.XXX	X.XXX	

N = number of patients in analysis set. % = percentages are calculated based on N as the denominator.

CI = Confidence interval; SE = Standard Error.

Notes: Sustained withdrawal of oxygen supplementation (in days) with no subsequent reutilisation during remaining study period is defined as the first day, from randomisation through completion of the study, on which a patient

i. satisfies categories 0 to 4 on the 11-point WHO Clinical Progression Scale, and

ii. has no subsequent reutilisation of oxygen supplementation (5 to 10 on the 11-point WHO Clinical Progression Scale)

[a] Those patients randomised to the control arm receiving the antiviral control arm (i.e., remdesivir or favipiravir).

[b] Calculated using the Kaplan-Meier estimator. CIs derived based on Brookmeyer-Crowley method and using a log log transformation.

[c] 2-sided p-values calculated using a stratified log-rank test, including the fixed effect of the treatment group and levels of the randomisation stratification factors, ie, geographical region (Europe vs. Rest of the World), Charlson Comorbidity Index (0-1 vs. >1) and pre-baseline Barthel index ( $\geq$ 90 versus <90) as derived using the eCRF data as covariates.

[d] Hazard Ratio, 95% CI and 2-sided p-values calculated using a stratified Cox proportional-hazards regression model, including the fixed effect of the treatment group and levels of the

randomisation stratification factors, ie, geographical region (Europe vs. Rest of the World), Charlson Comorbidity Index (0-1 vs.>1) and pre-baseline Barthel index (≥90 versus <90) as derived using the eCRF data as covariates. Hazard Ratio > 1 favours a Plitidepsin arm to be associated with a shorter time to sustained withdrawal of oxygen supplementation than Control Arm. [e] Statistics calculated relative to Control Arm.

Reference: Listing 16.2.6.5

Programming notes (not part of the table):

• Table template TEF011A.

- The displayed xxx do not reflect actual decimal precision. Please follow Section 2.11 for rounding rules.
- If 25th percentile, median or 75th percentile is not reached, present as "NR".

Variable	Plitidepsin 2.5mg (N=XXX)	Plitidepsin 1.5mg (N=XXX)	Control Arm without Antiviral [a] (N=XXX)
Patients who Reported Sustained Withdrawal of Oxygen			
Supplementation, n (%) Censored Patients, n (%)	xxx (xx.x) xxx (xx.x)	xxx (xx.x) xxx (xx.x)	xxx (xx.x) xxx (xx.x)
Time-to Sustained Withdrawal of Oxygen Supplementation (days) 95%			
CI [0] 25th percentile	xx x (xx x xx x)	xx x (xx x xx x)	xx x (xx x xx x)
Median	$\mathbf{X}$	$\mathbf{X} \mathbf{X} \mathbf{X} \mathbf{X} \mathbf{X} \mathbf{X} \mathbf{X} \mathbf{X} $	$\begin{array}{c} \mathbf{X}\mathbf{X}\mathbf{X} & (\mathbf{X}\mathbf{X},\mathbf{X},\mathbf{X}\mathbf{X}) \\ \mathbf{X}\mathbf{X}\mathbf{X} & (\mathbf{X}\mathbf{X},\mathbf{X},\mathbf{X}\mathbf{X}\mathbf{X}) \end{array}$
75th percentile	xx.x (xx.x, xx.x)	xx.x (xx.x, xx.x)	xx.x (xx.x, xx.x)
Mean (SE)	xx.x (xx.x)	xx.x (xx.x)	xx.x (xx.x)
Stratified Log-Rank Test			
2-sided p-value [c]	X.XXX	X.XXX	
Supportive Analysis - Stratified Cox Regression Model			
Hazard Ratio [d,e]	X.XXX	X.XXX	
95% CI for Hazard Ratio [d,e]	X.XXX - X.XXX	X.XXX - X.XXX	

#### Table 14.2.4.3.2 Time to Sustained Withdrawal of Oxygen Supplementation - Control Arm without Antiviral (Intent-To-Treat Population)

N = number of patients in analysis set. % = percentages are calculated based on N as the denominator.

CI = Confidence interval; SE = Standard Error.

Notes: Sustained withdrawal of oxygen supplementation (in days) with no subsequent reutilisation during remaining study period is defined as the first day, from randomisation through completion of the study, on which a patient

X.XXX

X.XXX

i. satisfies categories 0 to 4 on the 11-point WHO Clinical Progression Scale, and

ii. has no subsequent reutilisation of oxygen supplementation (5 to 10 on the 11-point WHO Clinical Progression Scale)

[a] Those patients randomised to the control arm without receiving the antiviral control arm (i.e., remdesivir or favipiravir).

[b] Calculated using the Kaplan-Meier estimator. CIs derived based on Brookmeyer-Crowley method and using a log log transformation.

[c] 2-sided p-values calculated using a stratified log-rank test, including the fixed effect of the treatment group and levels of the randomisation stratification factors, ie, geographical region (Europe vs. Rest of the World), Charlson Comorbidity Index (0-1 vs. >1) and pre-baseline Barthel index ( $\geq$ 90 versus <90) as derived using the eCRF data as covariates.

[d] Hazard Ratio, 95% CI and 2-sided p-values calculated using a stratified Cox proportional-hazards regression model, including the fixed effect of the treatment group and levels of the

randomisation stratification factors, ie, geographical region (Europe vs. Rest of the World), Charlson Comorbidity Index (0-1 vs. >1) and pre-baseline Barthel index ( $\geq$ 90 versus <90) as derived using the eCRF data as covariates. Hazard Ratio > 1 favours a Plitidepsin arm to be associated with a shorter time to sustained withdrawal of oxygen supplementation than Control Arm. [e] Statistics calculated relative to Control Arm.

Reference: Listing 16.2.6.5

2-sided p-value [d]

Programming notes (not part of the table):

• Table template TEF011A.

- The displayed xxx do not reflect actual decimal precision. Please follow Section 2.11 for rounding rules.
- If 25th percentile, median or 75th percentile is not reached, present as "NR".

